2.4.3.2 Compliance

A given administration will be considered noncompliant if the patient did not take the planned dose of treatment as required by the protocol. No imputation will be made for patients with missing or incomplete data. Treatment compliance will be calculated and presented for glimepiride or matching placebo (Capsule) and sotagliflozin or matching placebo (Tablet) separately by treatment group.

Percentage of compliance for a patient will be defined as the number of days that the patient was compliant to Capsule or Tablet, respectively, divided by the total number of days that the patient was planned to take IMP during the treatment epoch defined in [Section 2.1.4](#) (ie, from the first date to the last date of double-blind IMP administration).

Above-planned dosing percentage for a patient will be defined as the number of days that the patient took a higher dose level of Capsule or higher dose of Tablet than planned, respectively, divided by the total number of days that the patient was planned to take IMP during the treatment epoch.

Under-planned dosing percentage for a patient will be defined as the number of days that the patient took a lower dose level of Capsule or lower dose of Tablet than planned, respectively, divided by the total number of days that the patient was planned to take IMP during the treatment epoch.

Treatment compliance, above-planned, and under-planned dosing percentages will be summarized for Capsule and Tablet separately and descriptively as quantitative variables (number, mean, SD, median, minimum, and maximum). The percentage of patients whose compliance is <80% will be summarized separately for Capsule and Tablet. In addition, numbers and percentages of patients with at least one day above-planned dose will also be provided separately for Capsule and Tablet, as well as numbers and percentages of patients with (0, 20%], and >20% of days under-planned dose.

Cases of overdose (see study protocol for further details) will constitute AEs/SAEs and be analyzed as such. More generally, dosing irregularities will be listed in [Section 2.2.1](#).

2.4.4 Analyses of efficacy endpoints

Efficacy analyses will be performed on the ITT population using the efficacy assessments collected during the study, including those obtained after IMP discontinuation or introduction of rescue therapy, unless otherwise specified.

Missing data for efficacy analyses are identified through steps described in [Section 2.5.3](#).

2.4.4.1 Analysis of primary efficacy endpoint(s)

For the primary efficacy endpoint, the following null and alternative hypotheses will be tested:

- $H_0: \mu_T - \mu_C \geq 0.3\%$.
- $H_1: \mu_T - \mu_C < 0.3\%$.

Where μ_T and μ_C are the mean changes from Baseline in HbA1c at Week 52 for sotagliflozin and glimepiride groups, respectively.

The null hypothesis will be tested at a 1-sided alpha level of 0.025 using a non-inferiority margin of 0.3% of HbA1c change by comparing the upper bound of the 2-sided 95% CI for the adjusted mean treatment difference between sotagliflozin and glimepiride with 0.3%.

Primary analysis

The primary efficacy endpoint of change in HbA1c from Baseline to Week 52 will be analyzed by an Analysis of Covariance (ANCOVA) model using HbA1c values measured at baseline and Week 52 (observed or imputed). The missing data at endpoint will be imputed by multiple imputation (MI) methods as detailed below. To be concise, the following texts related to imputation are generalized to accommodate primary as well as continuous secondary efficacy endpoints.

Missing endpoint data at Week 52 or Week 26 (or Week 12 for SBP) visit will be imputed using a model built separately in each treatment group and estimated from the patients in the same treatment group who prematurely discontinue the IMP before the Week 52 or Week 26 (or Week 12 for SBP) visit but have measurements for the endpoint (ie, retrieved dropouts). The imputation model will include the randomization strata and the corresponding baseline value. In cases of non-convergence during the imputations, the offending stratum will be identified and then will be dropped from the model. Considering that the number of retrieved dropout patients in each treatment group is expected to be small, a simple imputation model based on regression will be used with baseline measurement included as the predictor. This will serve as the primary model of imputation for missing data should sampling criteria be satisfied (see below).

An alternative (back-up) imputation method will be used if the number of patients who prematurely discontinue the IMP before the Week 52 or Week 26 (or Week 12 for SBP) visit but have measurements for the endpoint is less than five (< 5) in any treatment groups (ie, insufficient number of retrieved dropouts to support the imputation method described above). This criterion will be assessed for each primary or continuous secondary efficacy endpoint separately.

In the back-up imputation method, missing post-baseline endpoint values at Week 52 or Week 26 (or Week 12 for SBP) will be imputed by the washout Multiple Imputation (MI) method under the missing not at random (MNAR) framework.

Missing endpoint data at the Week 52 or Week 26 (or Week 12 for SBP) in all treatment groups (sotagliflozin 200 mg and 400 mg, glimepiride and placebo) are imputed from a model estimated from patients in the placebo group who have the endpoint data available.

For patients in the sotagliflozin 400 mg, sotagliflozin 200 mg and glimepiride groups with missing data at Week 52 or Week 26 (or Week 12 for SBP), their missing values will be imputed using observed baseline and the observed primary endpoint data from placebo completers; no intermittent values from either placebo or the active treatment groups will be used.

For placebo patients, missing data will be imputed based on the placebo group data. Intermittent observed values will be used while imputing missing values at Week 52 or Week 26 (or Week 12 for SBP). In cases that a non-monotone missing data pattern occurs at the intermediate visits, these data points will be first imputed in the placebo group using the Markov Chain Monte Carlo

(MCMC) option in PROC MI to achieve a monotone missing pattern for all placebo patients. The Week 52 or Week 26 (or Week 12 for SBP) endpoint values will be subsequently imputed from the multiple copies of the original dataset where each copy will have a monotone missing pattern.

The imputation models for the washout MI method will include the randomization strata and the corresponding baseline value. Missing data will be imputed using the regression method.

In cases of non-convergence during the imputations, especially for the MCMC application in the placebo non-monotone datasets, graphical measures (eg, trace and autocorrelation plots) will be used to identify the offending variable and once detected, that variable(s) will be dropped from the model and the imputations will be re-run. These re-run models will use the same seed number and number of imputations as used in the original models.

Using either imputation method, missing endpoint data will be imputed 2000 times to generate multiple datasets with complete data. Other details of the imputation procedures such as the seed number and sort ordering are specified in the SAS programs. The change from baseline to Week 52 (or Week 12 for SBP) will be derived from observed and imputed HbA1c values at Week 52 (or Week 12 for SBP). Each of the complete datasets after the imputation will be analyzed using the ANCOVA model with treatment groups (sotagliflozin 400 mg, sotagliflozin 200 mg, glimepiride, and placebo groups), randomization stratum of HbA1c at Screening ($\leq 8.5\%$, $> 8.5\%$), randomization stratum of SBP at Screening (< 130 mmHg, ≥ 130 mmHg), and country as fixed factors, and baseline HbA1c value as a covariate. Results from each analysis will be combined using Rubin's formula to provide the adjusted mean change in HbA1c from Baseline to Week 52 (or Week 12 for SBP) for each treatment group, as well as the between-group differences and their associated 95% CIs. If the upper bound of the 2-sided 95% CI for the adjusted mean difference (sotagliflozin 400 mg versus glimepiride) in HbA1c change from Baseline to Week 52 is $< 0.3\%$, then non-inferiority will be declared.

Sensitivity analyses

A sensitivity analysis will be conducted with the 52-week treatment completers (ie, all patients who complete the 52-week Treatment Period and do not start rescue therapy) using the Week 52 values and the same missing data imputation method (washout imputation method) and ANCOVA model described above.

Tipping-point analysis based on the same MI method as applied to the primary analysis will be performed to examine the robustness of the results from the primary analysis. Patients who were randomized to sotagliflozin 400 mg group and had no HbA1c data at Week 52 will be given a penalty. The penalty will be gradually increased to evaluate at which level the conclusion of the analyses in terms of statistically non-inferior to glimepiride is changed. The tipping point is the penalty level, at which the magnitude of efficacy reduction in patients without HbA1c data at Week 52 creates a shift in the treatment effect of sotagliflozin 400 mg from being statistically non-inferior to glimepiride to statistically inferior to glimepiride. Least-squares (LS) mean difference between sotagliflozin and glimepiride and its associated 95% CI will be provided for each penalty level. The steps to perform the tipping point analysis are as follows:

1. Missing data will be imputed using the same MI method as applied to the primary analysis.
2. The imputed HbA1c value at Week 52 in the sotagliflozin 400 mg group will be penalized by adding a penalty δ (eg, $\delta = 0.1\%$) in each complete dataset.
3. Change from Baseline at Week 52 in HbA1c will be analyzed using the same ANCOVA model as specified in the primary analysis in each complete dataset.
4. Results will be combined across complete datasets using Rubin's formula.
5. For noninferiority of sotagliflozin 400 mg versus glimepiride on HbA1c reduction, Steps 2 to 4 will be repeated with incremental penalty at δ (ie, $\delta, 2\delta, 3\delta, \dots$) until the upper bound of the 2-sided 95% CI for the adjusted mean difference is $\geq 0.3\%$. The range of penalty values will include the non-inferiority margin of 0.3% to evaluate bias toward the null.
6. For superiority of sotagliflozin 400 mg versus placebo on HbA1c reduction, steps 2 to 4 will be repeated with incremental penalty at δ (ie, $\delta, 2\delta, 3\delta, \dots$) until the p-value for treatment effect of sotagliflozin 400 mg compared to placebo estimated in Steps 2 to 4 is ≥ 0.05 .

The tipping point analysis will be performed on the ITT population and completer's population. Similarly, the tipping point analysis will be conducted for the sotagliflozin 400 mg versus glimepiride non-inferiority endpoint only if the primary efficacy endpoint analysis yields a statistically significant finding and the upper bound of the 2-sided 95% CI associated with the non-inferiority test is $< 0.3\%$.

In addition to the tipping point analyses, if the retrieved dropout imputation is applied to the primary analysis, the analysis based on the washout imputation (ie, the backup imputation method) will be presented as a sensitivity analysis.

Assessment of treatment effect by subgroup

Descriptive analyses will be performed on the primary endpoint to summarize the treatment effects across subgroups defined by the following Baseline or Screening factors:

- Race (White, Black or African American, Asian, Other) (any race groups with fewer than 5 patients may be combined with "Other" category as appropriate).
- Ethnicity (Hispanic, Not Hispanic).
- Age group (< 50 years, ≥ 50 to < 65 years, ≥ 65 years) (any category with fewer than five patients may be combined with another category as appropriate).
- Gender (Male, Female).
- Baseline BMI level ($< 30, \geq 30$ kg/m²).
- Baseline HbA1c ($\leq 8.5\%, > 8.5\%$).
- Baseline SBP (< 130 mmHg, ≥ 130 mmHg).

- Baseline eGFR (≥ 30 to < 60 mL/min/1.73 m² [Moderate decrease in GFR], ≥ 60 to < 90 mL/min/1.73 m² [Mild decrease in GFR], and ≥ 90 mL/min/1.73 m² [Normal]).
- Duration of diabetes (< 10 , ≥ 10 years).
- Country.

The treatment effects (sotagliflozin 400 mg versus glimepiride) across the subgroups defined for each of these factors will be estimated for the change from Baseline to Week 52 in HbA1c in the ITT population, and using the retrieved dropouts method if there are at least 5 patients in each study treatment group who discontinued but have the endpoint. Otherwise, the washout imputation method will be used. The ANCOVA model will include treatment groups (sotagliflozin 400 mg, sotagliflozin 200 mg, glimepiride, and placebo), randomization stratum of HbA1c at Screening ($\leq 8.5\%$, $> 8.5\%$), randomization stratum of SBP at Screening (< 130 mmHg, ≥ 130 mmHg), subgroup factor, treatment-by-subgroup factor and country as fixed factors, and baseline HbA1c value as a covariate. The adjusted estimates of treatment mean differences (sotagliflozin 400 mg versus glimepiride) with standard error (SE) and 95% CIs will be provided as appropriate across the subgroups. A graphical presentation of the results (ie, forest plot) will also be provided.

In the event that the subgroup factor is identical or similar to a randomization strata factor (eg, Baseline HbA1c category or Baseline SBP category) or country, only the subgroup factor (as a single factor or an interaction term) will be included in the model in order to avoid the issue of collinearity in the analysis. The corresponding strata factor or country will not be included in the model.

Summary statistics at scheduled visits

Summary statistics (for screening value, baseline value, observed postbaseline value and its changes from baseline) at scheduled visits will be provided for each treatment group. The summary will include the number of observations, mean, SD, SE, minimum, median, and maximum. Graphical presentations will also be used to examine trends over time using mean values (\pm SE) and mean changes from baseline (\pm SE) at each of the scheduled visits.

Similar presentations will be provided excluding measurements after rescue therapy during the 52-week double-blind treatment period.

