1.3 DETERMINATION OF SAMPLE SIZE

The sample size/power calculations were performed based on the primary endpoint of change of HbA1c from Baseline to Week 52 in the intent-to-treat (ITT) population. Assuming a common standard deviation (SD) of 1.1%, and the true difference between sotagliflozin 400 mg and glimepiride is zero, 310 patients in the sotagliflozin 400 mg and glimepiride groups will ensure that the upper bound of the 2-sided 95% confidence interval (CI) of the adjusted mean difference is below 0.3% with at least 90% power. This sample size will have 80% power to test the non-inferiority of change of HbA1c from Baseline to Week 52 in completers, with a 30% dropout rate.

A sample size of 310 patients in sotagliflozin 400 mg group and 155 patients in placebo group will have more than 99% power to detect a treatment difference of 0.6% in mean HbA1c change from Baseline to Week 26 between sotagliflozin 400 mg and placebo (SD 1.2%; 2-sided 5% significance level).

A sample size of 155 patients in sotagliflozin 200 mg group and 155 patients in placebo group will have 95% power to detect a treatment difference of 0.5% in mean HbA1c change from Baseline to Week 26 between sotagliflozin 200 mg and placebo (SD 1.2%; 2-sided 5% significance level).

The total sample size is 930 patients to be randomized (sotagliflozin 400 mg group: 310; sotagliflozin 200 mg group: 155; glimepiride: 310; placebo: 155).

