- Non-inferiority comparison of sotagliflozin 200 mg and glimepiride on change from Baseline to Week 52.
- Superiority comparison of sotagliflozin 400 mg and glimepiride on change from Baseline to Week 52.

Missing data will be imputed at Week 26 or Week 52 as appropriate. The sotagliflozin groups will be penalized incrementally by a penalty, and repeated until the upper bound of the 2-sided 95% CI is $\geq 0.3\%$ for the non-inferiority comparison or until the p-value for treatment effect between the two treatment groups is >0.05 for the superiority comparison, respectively.

The tipping-point analysis will be performed only if the respective secondary endpoint comparison is statistically significant at a two-sided $\alpha = 0.05$.

A sensitivity analysis will also be conducted with the treatment completers (ie, all patients who complete the 26-week double-blind treatment period and do not start rescue therapy) for noninferiority of sotagliflozin 400 mg versus glimepiride on HbA1c reduction using the same ANCOVA model described in [Section 2.4.4.1](#). The washout imputation method will be used, where missing endpoint data in all treatment groups are imputed from a model estimated from patients in the placebo group who have the endpoint data available. The imputation model will include the randomization strata and the corresponding baseline value. Missing data will be imputed using the regression method.

Assessment of treatment effect by subgroup

Similar to that is described in [Section 2.4.4.1](#), the treatment effects for the following treatment group comparisons across subgroups will be estimated for the change from Baseline in HbA1c in the ITT population, and using the same MI method for the primary endpoint analysis:

- Sotagliflozin 400 mg group vs. placebo group at Week 26.
- Sotagliflozin 200 mg group vs. placebo group at Week 26.
- Sotagliflozin 200 mg group vs. glimepiride group at Week 52.

The ANCOVA model will include treatment groups (sotagliflozin 400 mg, sotagliflozin 200 mg, glimepiride, and placebo groups), randomization stratum of Screening HbA1c ($\leq 8.5\%$, $>8.5\%$), randomization stratum of Screening SBP (<130 mmHg, ≥ 130 mmHg), subgroup factor, treatment-by-subgroup factor, and country as fixed factors and using baseline HbA1c value as a

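### SAP 2.4.4.1 gives two conflicting predictor sets for the retrieved-dropout imputation model, and the choice matters for Week 26 power when an arm is near the permitted minimum of five such patients

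*SAP*

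**What the plan says.** The retrieved-dropout paragraph of SAP 2.4.4.1 builds one model per arm, estimated from patients of that arm who left study drug early but have the endpoint measurement. It then describes the predictors twice.

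- First: "The imputation model will include the randomization strata and the corresponding baseline value". This is followed by "In cases of non-convergence during the imputations, the offending stratum will be identified and then will be dropped from the model".
- Then, with the small expected number of retrieved dropouts given as the reason: "a simple imputation model based on regression will be used with baseline measurement included as the predictor". The next sentence calls this the primary imputation model, provided the sampling criteria are met.

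The washout method replaces it only if the number of retrieved dropouts is "less than five (< 5) in any treatment groups", judged separately for each endpoint. SAP 2.4.4.2 and 2.5.2 apply the same threshold to the continuous secondary endpoints. There are 2000 imputations, an ANCOVA that includes both strata, and Rubin's rules.

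The strata sentence also appears for the washout model: "The imputation models for the washout MI method will include the randomization strata and the corresponding baseline value" in 2.4.4.1, and "The imputation model will include the randomization strata and the corresponding baseline value. Missing data will be imputed using the regression method" in 2.4.4.2. On programming, the SAP says "Other details of the imputation procedures such as the seed number and sort ordering are specified in the SAS programs".

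SAP 1.3 states that the 200 mg versus placebo comparison "will have 95% power to detect a treatment difference of 0.5% in mean HbA1c change from Baseline to Week 26". It gives more than 99% for 400 mg versus placebo at a difference of 0.6%.

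**The concern.** Two programmers could follow this paragraph and fit different main analyses. No visible sentence ranks the two descriptions. SAP 2.4.4.2, 2.5.2 and Appendix D name the method without listing predictors.

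The difference is not cosmetic at the permitted minimum. Intercept, baseline and two two-level strata are four parameters, to be fitted to as few as five patients. The stratum-drop rule gives no protection. It is triggered by non-convergence, and a least-squares fit with one residual degree of freedom is closed-form and simply runs.

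The exposure is mainly at Week 26, where an arm can plausibly have few retrieved dropouts. The 200 mg versus placebo test is seventh of twelve in the fixed sequence of SAP 2.4.4.4, so a failure there stops the five tests after it.

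**Working it through.** **1. Stated power, no missing data** (inputs from SAP 1.3; normal approximation).

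- 200 mg vs placebo: SE = 1.2 × √(1/155 + 1/155) = 0.136; 0.5/0.136 = 3.67; 3.67 − 1.96 = 1.71; power 95.6% (stated 95%).
- 400 mg vs placebo: SE = 1.2 × √(1/310 + 1/155) = 0.118; 0.6/0.118 = 5.08; 5.08 − 1.96 = 3.12; power 99.9% (stated above 99%).
- Week 52 non-inferiority: SE = 1.1 × √(2/310) = 0.088; 0.3/0.088 = 3.40; 3.40 − 1.96 = 1.44; power 92.4% (stated at least 90%).

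**2. What the imputation draws.** Regression imputation draws the residual variance as SSR/χ²(ν), where ν is patients minus parameters. Its expectation is σ² × ν/(ν − 2), which is finite only if ν exceeds 2.

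| Retrieved dropouts in arm | ν, strata kept | multiplier of σ² | ν, baseline only | multiplier of σ² |
|---|---|---|---|---|
| 5 | 1 | no finite mean | 3 | 3.0 |
| 6 | 2 | no finite mean | 4 | 2.0 |
| 8 | 4 | 2.0 | 6 | 1.5 |
| 10 | 6 | 1.5 | 8 | 1.33 |
| 15 | 11 | 1.22 | 13 | 1.18 |

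A stratum that is constant or aliased in the arm drops out. In simulated five-patient arms ν was 1 in 76–80% of cases and 2 in 20–23%. The four-arm ANCOVA pools its residual variance, so one such arm affects every contrast.

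**3. Simulated Week 26 power, 200 mg vs placebo.** SD, difference and arm sizes are from SAP 1.3. Assumed: the missing rates and retrieved-dropout counts shown, retrieved dropouts and missing patients like the rest of their arm, the baseline and stratum distributions, and country omitted. Counts are per 155-patient arm / 310-patient arm. Ranges span separately programmed simulations.

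| Retrieved dropouts | Missing | Strata kept | Baseline only |
|---|---|---|---|
| 5/10 | 5% | 4–7% | 82–89% |
| 5/10 | 10% | 2–4% | 58–62% |
| 5/10 | about 12% | about 5% | about 48% |
| 6/12 | 5% | 47–61% | 90–95% |
| 8/16 | 5% | 91% | 94% |
| 8/16 | 10% | 62–71% | 84–85% |
| 10/20 | 5% | 92% | 94% |
| 10/20 | 10% | 81% | 85% |

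With 15 retrieved dropouts in every arm and 10% missing, the figures are 90% and 91%. For 400 mg vs placebo at 5/10 and 5% missing they are 8–15% and 98–99%.

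**4. Which cells are plausible.** The only dropout figure is 30%, used in SAP 1.3 for Week 52 completers. If it is spread evenly, 155 × 0.30 × 26/52 = 23.25 patients per small arm stop by Week 26. If 20–80% of them return (assumed), that is 4.7 to 18.6 retrieved dropouts. On this basis five returners leave 18.25/155 = 11.8% missing, eight leave 15.25/155 = 9.8%, and fifteen leave 8.25/155 = 5.3%. Five returners with only 5% missing needs (5 + 7.75)/155 = 8.2% stopping by Week 26.

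If counts vary as Poisson and the method is used, the chance that the smallest arm has exactly five is 21% at 6 expected per small arm, 16% at 8 and 2.5% at 12. Averaged over such counts at 5% missing, power is 50% vs 90% (6 expected), 70% vs 92% (8), 82% vs 92% (10) and 92% vs 94% (15). These gaps exceed the fixed-count rows because some trials fall to five or six.

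**5. Week 52 primary and error rate.** The same dropout assumption gives 155 × 0.30 × (0.2 to 0.8) = 9.3 to 37.2 retrieved dropouts. Averaged power, strata vs baseline only, at 5% and 10% missing: 82 vs 91% and 72 vs 84% at 9.3 expected; 88 vs 91% and 81 vs 85% at 12; within one point from 18.6. Type I error at 5/10 is 0.2% (strata) and 2.6% (baseline only) for the two-sided Week 26 test, and 0.0% and 1.0% for non-inferiority at a true difference of 0.3%.

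**The case against.** The best reply is that the paragraph already answers the question. The baseline regression comes last, names a single predictor, gives small samples as its reason and is called the primary model. That stands as the more natural reading. It is not conclusive. It leaves the strata sentence and the stratum-drop rule with no purpose. The word *primary* is set against the back-up washout method, so it may refer to the retrieved-dropout approach as a whole. Listing baseline as included does not exclude the strata. The strata sentence suits the larger placebo sample behind the washout model and may have been carried over from there. That is a reason to delete it, but the text does not say so.

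Second, the collapse is a corner of the less natural reading, confined to about five or six retrieved dropouts. This also stands. The five-dropout cell at 5% missing needs less dropout than an even spread of 30%. In the consistent cell near 12% missing, the baseline-only model does poorly too.

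Third, several Table 2 rows for SAP versions 2 and 3 are redacted, so the point covers the visible text only. The programs may fix one model, but the SAP assigns them details of the seed and sort-order kind and does not mention the predictors.

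Fourth, the retrieved-dropout counts were knowable after the lock of 12Sep2019. The averaged figures therefore describe the plan and not what happened in the trial.

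**Conclusion.** The conflict is real and should be resolved in the text. If the strata are kept, an arm at five retrieved dropouts loses nearly all of the stated Week 26 power. The loss is substantial at six and moderate at eight. It is negligible from about ten at 5% missing, or about fifteen at higher rates. The direction follows from the degrees of freedom alone. The sizes rest on assumed missing rates and counts, since the documents give none for Week 26.

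A reader might infer more than the documents support:

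- That the SAP prescribes the strata model. It does not; the baseline-only statement is the likelier intent.
- That the primary result is in danger. The Week 52 test is affected only if retrieved-dropout counts are low, and SAP 2.4.4.1 presents the washout analysis beside it.
- That false-positive risk rises. Both versions are conservative at the minimum.
- That choosing baseline only secures the stated power. At five retrieved dropouts it does not.

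**What to change.** In the retrieved-dropout paragraph of SAP 2.4.4.1, delete the sentence "The imputation model will include the randomization strata and the corresponding baseline value" and the one after it on dropping a stratum. At "a simple imputation model based on regression will be used with baseline measurement included as the predictor", add that no other covariate enters the model. Leave the washout paragraphs in 2.4.4.1 and 2.4.4.2 as they are.

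The database locked on 12Sep2019 and this SAP version is dated 03-Apr-2020. The change therefore needs a dated Table 2 row that records it as a post-lock resolution of a text conflict, made without reference to treatment effects. If the programs used the strata, disclose that and show that version as a sensitivity analysis. Rewriting the SAP to match the programs could write in the weaker model.

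The cost is two sentences and, if the strata were programmed, two model terms. The downside is that the imputation no longer conditions on the SBP stratum. For HbA1c endpoints the HbA1c stratum is largely carried by baseline HbA1c. Whether five is a high enough minimum is a separate question that this edit does not settle.
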